6. GENERAL STATISTICAL ISSUES

All confidence intervals will be two-sided with 95% coverage. Likewise, all significant tests will be two-sided and at 0.05 significance level.

Potential outliers will be identified by looking at summary statistics and scatter plots as needed. All outliers will be verified as-such from the source documentation. If excluding one (or several) outlier(s) change(s) the interpretation of the data, two summaries and analyses will be done, one with and one without the outlier(s).

Missing data will be treated as missing at random unless available evidence indicated that missing data is informative. If a participant has missing data at a specific time point, data at all non-missing time points will be used and included in relevant analyses. For the primary analysis of pregnancy outcomes, participants who discontinue early (including participants who were lost to follow-up) will be included but will be censored on the date of their last known pregnancy status when still using the received study product.

All comparisons between treatment groups will be made without adjustment for multiple comparisons. All statistical analyses will be done using SAS® (SAS Institute Inc., Cary) Version 9.4 (or higher).

7. STATISTICAL ANALYSIS

7.1. Study Participant Disposition and Follow-up

Information about study participant disposition and follow-up during the study will be provided and summarized for each treatment group as follows:

- A flowchart will document the flow of participants through the study and relate this to the different analysis populations;
- Tables will summarize:
 - the number and percentage of participants screened, randomized, attempt insertion, first attempt insertion, the second attempt insertion, successful insertion, insertion failure, early method discontinuation and its reasons, and protocol deviation/violation by study site and overall, incidence of uterine perforation, and IUD expulsion (complete and partial);
 - o the reasons for participant non-eligibility for each of the populations;
 - o the number and percentage of participants included in each of the analysis populations by study treatment;
 - o the number and percentage of total study visits completed, person-years completed, and participant end of study status as indicated in the End of Trial form.
 - o the person-years with IUD in place by study group.

The similarity of participant end of study status between treatment groups will be evaluated using Mantel-Haenszel tests, stratified by site.

7.2. Analysis of Baseline Data

Baseline variables will be summarized for the ITT, User, Per Protocol and Efficacy Analysis populations, and for the Treated and Lost to Follow-Up Populations under the condition stated in Section 5. The following baseline measures collected at the screening and enrolment visits will be summarized by treatment group:

- Demographic data: age, ethnicity, race, parity, marital status, level of education
- Vital signs
- Substance use: tobacco use, alcohol use, marijuana use and illicit drug use
- Medical history including prior and concomitant medications
- Gynecological history

- Infection history (Pre-treatment signs and symptoms of: (urinary tract infection, yeast infection, bacterial vaginosis, pelvic infection, Endometriosis, and STIs)
- Contraceptive history
- Pregnancy history

Data will be presented in summary tables by treatment group, site and overall. Categorical variables, and continuous variables that have been categorized at discrete levels, will be summarized by frequencies and percentages. Continuous variables will be summarized by means, standard deviations, medians, interquartile ranges, minima and maxima.

7.3. Analysis of Primary Endpoint - Efficacy Data

Efficacy data will be analyzed on the Efficacy Analysis Population. The primary efficacy analysis will include those women under 36 years old at time of enrollment who are in the Mona Lisa NT Cu380 Mini group.

Additional efficacy analyses will include the following groups

- nulliparous women under 36 years old at time of enrollment who are in the Mona Lisa NT Cu380 Mini group
- parous women under 36 years old at time of enrollment who are in the Mona Lisa NT Cu380 Mini group
- all women who are in the Mona Lisa NT Cu380 Mini group, regardless of age and parity status
- nulliparous women under 36 years old at time of enrollment who are in the ParaGard group
- all women who are in the ParaGard group, regardless of age or parity status.

No formal statistical comparisons will be conducted between above groups.

7.3.1 Definition of variables

Pregnancy: The endpoint of the primary objective is incident pregnancy. The following data will be examined to determine whether a pregnancy has occurred:

- Positive pregnancy test result recorded on the Pregnancy Test, Pregnancy Notification, or Pregnancy Outcomes forms;
- Pregnancy otherwise reported on Adverse Event, IUD Removal or End of Trial forms.

Estimated Date of Conception (EDC): The Investigator will estimate the date of conception based upon results of transvaginal ultrasound examination, quantitative β -hCG determination, last menstrual period (per daily diary information), pelvic and/or abdominal examination, and pregnancy outcome.

Without looking at the treatment group assignment in the LiveTrial eCRF, the Medical Monitors will review the assigned date of conception and other relevant data to confirm the date of conception to be used for analysis. If the Medical Monitors assign a different date during this adjudication process, their reason for assigning a different date will be documented.

On-treatment Pregnancy: An on-treatment pregnancy is a pregnancy in which the EDC is 1) on or after the date of IUD insertion and 2) on or before 7 days of post IUD removal. In addition, a "worse case" scenario will be used that considers pregnancies as "on-treatment" if the EDC or date of expulsion is not known.

Study Cycle (28-day equivalent): Every 28 study days with information about whether the participant used other contraceptive methods within those 28 study days will be considered as a study cycle (e.g., study day 28 will be considered the end of cycle 1, and day 56 for the end of cycle 2, etc., so long as information on use of other methods is documented for those periods). Note: cycles where conception occurred or where a participant had the IUD removed will be considered 'study cycles' (even if the EDC or removal did not occur on the 28th day), so long as there is information on other contraceptive methods use up until the time of conception defined as an on-treatment pregnancy or IUD removal.

Study Cycles (described previously) with no diary data will be excluded from the pregnancy analysis. Two types of pregnancy analysis cycle will be used for the efficacy analysis:

Primary Pregnancy Analysis Cycle: A primary pregnancy analysis cycle is a study cycle that

- 1. contains an on-treatment pregnancy, or
- 2. has both these characteristics:
 - a. reported sexual intercourse in the cycle and
 - b. no reported use of other contraceptives in the cycle

The primary pregnancy analysis cycles will be used for the primary efficacy analysis.

Secondary Pregnancy Analysis Cycle: A secondary pregnancy analysis cycle is a study cycle that

- 1. contains an on-treatment pregnancy, or
- 2. has no reported use of other contraceptives in the cycle

The secondary pregnancy analysis cycles will be used for the sensitivity efficacy analysis.

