5.6. Efficacy Analysis Population

The Efficacy Analysis Population is a subset of the User Population that includes women who provide at least one valid pregnancy analysis cycle as defined in Session 8.3.1. This analysis population will be used for analyzing the pregnancy endpoint. The subpopulation under 36 years old at enrollment who are in the Mona Lisa NT Cu380 Mini group and provide at least one cycle

with documented intercourse and no use of other methods will be the primary population for estimating efficacy (per FDA directives).

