7.3.2 Statistical methods

The on-treatment pregnancy rate will be estimated using the primary pregnancy analysis cycles based on the Pearl Index (pregnancies per 100 woman-years of follow-up)

$$Pearl\ Index = \frac{Number\ of\ Pregnancies}{Total\ Number\ of\ Pregnancy\ Analysis\ Cycles} \times 1300$$

and its exact 95% confidence interval (CI) derived using a Poisson distribution assumption as

Lower 95% CI (Pearl Index)
$$= \frac{\chi_{0.025, df=v1}^{2}}{2 \times Total \ Number \ of \ Pregnancy \ Analysis \ Cycles} \times 1300$$

and

Upper 95% CI (Pearl Index)
$$= \frac{\chi_{0.975, df=v2}^{2}}{2 \times Total \ Number \ of \ Pregnancy \ Analysis \ Cycles} \times 1300$$

where $v1=2 \times \text{Number of Pregnancies and } v2=2 \times (\text{Number of Pregnancies} +1)$. Analysis will be done for each year of use and cumulatively through year three.

In addition, the typical use Pearl Index estimated by including all Study Cycles in the denominator of Pearl Index estimator will be reported. Similarly, by using all Study Cycles, the Kaplan-Meier product limit method with cycle as the "time" unit will also be used to summarize the typical use cumulative probability of pregnancy through the study follow-up period. Ninety five percent confidence intervals about the estimates of the cumulative probability of pregnancy will be provided, using the method of Peto et al. to calculate the standard error for the probabilities. Moreover, two additional sensitivity analyses will be considered to handle those cycles using other contraceptive methods in the Kaplan-Meier product limit method. The first approach is to exclude those cycles from the analysis and the remaining cycles will be renumbered to provide contiguous cycles (e.g., if Cycle 3 is excluded, Cycle 4 will be treated as Cycle 3, and so forth). The second approach is to allow participants to leave and re-enter the risk set of pregnancy of the Kaplan-Meier product limit method if they had a cycle using other contraceptive methods between two primary pregnancy analysis cycles.

In a separate analysis, these same approaches will be applied to analyze pregnancy using secondary pregnancy analysis cycles.

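### SAP 7.3.1, read literally, drops a confirmed on-treatment pregnancy from the primary Pearl Index when its conception cycle has no contraceptive-use record

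*SAP*

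**What the plan says.** SAP 7.3.1 builds the analysis in layers.

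- **Event.** A pregnancy is on-treatment if conception falls on or after insertion and "on or before 7 days of post IUD removal". A worst-case rule also treats it as on-treatment "if the EDC or date of expulsion is not known". Neither condition mentions a record of other contraceptive use.
- **Study cycle.** A 28-day period qualifies only if other-method use in it is documented. A cycle containing a conception or a removal qualifies even if it ends early, but again only "so long as there is information on other contraceptive methods use up until the time of conception"; the sentence goes on to name IUD removal as the alternative end point.
- **Exclusion.** "Study Cycles (described previously) with no diary data will be excluded from the pregnancy analysis". Pregnancy cycles are not exempted.
- **Analysis cycle.** "A primary pregnancy analysis cycle is a study cycle that" either contains an on-treatment pregnancy (item 1), or has reported intercourse and no reported other method (item 2). The secondary cycle has the same structure without the intercourse condition.

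SAP 7.3.2 estimates the rate from the primary analysis cycles. The numerator of its formula is simply the number of pregnancies; only the denominator is tied to analysis cycles. The typical-use index is obtained "by including all Study Cycles in the denominator of Pearl Index estimator will be reported", with nothing said about its numerator. The main Kaplan-Meier analysis uses study cycles. On timing, "Analysis will be done for each year of use and cumulatively through year three".

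SAP 5.6 adds that the subgroup who provide at least one cycle "with documented intercourse and no use of other methods will be the primary population" for efficacy, citing FDA directives. Protocol 19.2.1 excludes cycles in which women report another method and does not mention cycles with no record.

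**The concern.** The record requirement comes before item 1. Item 1 keeps a pregnancy cycle without asking for reported intercourse or absence of other methods, but the cycle must already be a study cycle, and that requires the record. A pregnancy that the Medical Monitors have confirmed and dated as on-treatment can therefore leave the primary analysis because a form is missing.

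No other planned analysis clearly recovers it. The secondary-cycle analysis and the Kaplan-Meier estimates also rest on study cycles, and the numerator of the typical-use index is not defined.

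The primary result is a single-arm rate with its interval, and the protocol's planning table runs from 0 to 6 pregnancies, so one event more or less shows in the report. An analyst who follows the nested definitions and one who follows the event definition and the formula could report different primary results from the same data. Any departure from the literal rule would be decided with the pregnancies already known.

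**Working it through.** **1. Reproduce the planning figure.** Protocol 19.1 gives about 17,700 cycles for women under 36: 800 randomized, 13 cycles a year, 84.3% evaluable, about 20% discontinuation a year, 37 months. Protocol 9.1 puts about 10% of women at 36-40, which leaves 720.

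Cycles = 720 × 13 × 0.843 × (1 − e^(−rT))/r, with T = 37/12.

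- r = −ln 0.8: 17,590, split 7,072 / 5,658 / 4,860 by year. The synopsis footnote gives 7,100 / 5,700 / 4,900.
- r = 0.2 as a hazard: 18,158, which is 2.6% above the stated total.

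With SAP 7.3.2, index = k × 1300/N and upper limit = χ²(0.975, 2(k+1))/2 × 1300/N. For k = 6 and N = 17,700: 6 × 1300/17,700 = 0.441, interval 0.162 to 0.959. Table 09 shows 0.4 (0.2-1.0). All seven rows of the table reproduce after rounding.

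**2. Effect of one pregnancy counted or dropped.**

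| Cycles | Pregnancies | Index | Upper limit |
|---|---|---|---|
| 17,700 | 7 | 0.514 | 1.059 |
| 17,700 | 6 | 0.441 | 0.959 |
| 17,700 | 5 | 0.367 | 0.857 |
| 19,470 | 7 | 0.467 | 0.963 |
| 19,470 | 6 | 0.401 | 0.872 |

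The second total is 17,700 × 880/800, a pro rata assumption for the amended sample size. At 17,700 cycles one event moves the index by about 0.07 and the upper limit by about 0.10. Adding the conception cycle to the denominator (17,701) changes nothing at three decimals.

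**3. By year of use, 1 event instead of 0.**

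| Year | Cycles | Index | Upper limit |
|---|---|---|---|
| 1 | 7,100 | 0 to 0.18 | 0.68 to 1.02 |
| 2 | 5,700 | 0 to 0.23 | 0.84 to 1.27 |
| 3 | 4,900 | 0 to 0.27 | 0.98 to 1.48 |

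**4. How often.** The documents give no rate of missing records in conception cycles. If it were 2%, 5% or 10% (assumed, independent between women), the chance that at least one of 6 pregnancies is affected, 1 − (1 − m)⁶, is 11%, 26% or 47%.

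**5. Direction under the literal rule.** An undocumented cycle also leaves the denominator, so the expected index is multiplied by (1 − mc)/(1 − mo), where mc and mo are the missing-record rates in conception cycles and other cycles. With mo = 5% (assumed), the factor is 0.84, 0.95, 1.00, 1.03 or 1.05 for mc = 20%, 10%, 5%, 2% or 0%. It can fall either side of 1.

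**The case against.** **The rule is already written.** The sentence introducing the formula refers to primary analysis cycles, and these are nested in study cycles. The two readings are not equally strong: the literal text points to exclusion. That stands. What remains is that the literal rule removes confirmed failures, and that it sits badly with the event definition, with item 1 and with the formula's unqualified numerator.

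**Few pregnancies would be affected.** A pregnancy should trigger all Early Discontinuation procedures (Protocol 13), which include collecting the outstanding forms (11.4, Table 06). The Follow Up Form also asks about other contraception (10.3.1), and the study-cycle definition names no particular form. This also stands.

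**The literal rule treats all cycles alike.** It is unbiased if records are missing equally often in conception and other cycles, whereas counting every pregnancy leans high. That is correct, and it is why both results should be reported.

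**The post-removal window.** A reader might infer that a conception within 7 days after removal can fall in a further 28-day interval for which no form is scheduled. The documents do not establish this. The full sentence in 7.3.1 gives IUD removal as an alternative end point, so information up to removal may be enough, and nothing says that such a conception needs another interval with its own record.

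**Conclusion.** The concern holds as a defect of the primary definition. Read literally, SAP 7.3.1 can take an adjudicated on-treatment pregnancy out of the primary Pearl Index, the secondary-cycle analysis and the Kaplan-Meier analysis for want of a record, against other parts of the same SAP. One such case changes the cumulative index by about 0.07 and its upper limit by about 0.10 at the planned cycles, and the yearly upper limits by about 0.3 to 0.5.

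Two stronger conclusions are tempting and not supported. The first is that the rule makes the device look better than it is: the direction depends on missing-record rates that the documents do not give. The second is that a pregnancy dropped at 7 would turn a failed trial into a successful one: the value 1.0 is a planning figure in Protocol 19.1, not a success threshold.

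The SAP 5.6 mismatch is narrow. It affects only a woman with no other qualifying cycle, because one qualifying cycle is enough for entry. The sizes assume the planned cycle totals. The trigger should be rare, but the primary endpoint is affected and the remedy is short, so the SAP should be changed.

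**What to change.** In SAP 7.3.1, state that every adjudicated on-treatment pregnancy in a woman under 36 in the Mona Lisa group counts in the primary numerator, with its cycle in the denominator, whatever the record status. Apply the other-method information and diary-data requirements to non-pregnancy cycles only.

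Align SAP 5.6 with item 1 of 7.3.1 by admitting a woman on the strength of an on-treatment pregnancy, subject to the FDA directives cited there.

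Report how many pregnancies depend on the rule. As a sensitivity analysis, give the Pearl Index restricted to documented cycles in both numerator and denominator.

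Editorial clarifications, to make at the same time:

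- Refer to the Other Contraceptive Use Form alongside the diary, since the diary stops at 12 months (Protocol 10.3.2, 10.3.3).
- Say whether worst-case pregnancies enter the primary analysis and, where the conception date is unknown, to which cycle they are assigned.
- Say that the typical-use numerator is the same set of pregnancies.

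The cost is a few sentences, one count and one table row. The primary estimate becomes slightly less favourable. If records are missing at random with probability m, it leans high by about 1/(1 − m): 1.02, 1.05 or 1.11 at m = 2%, 5% or 10% (assumed). The documented-cycles analysis has no such lean when the missing rates are equal, so reporting both shows its size.

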# 10.3.2 Daily Diary

For the first 12 months of use, participants will maintain a daily diary to record bleeding/spotting. Each form will collect one cycle of information consisting of 28 days of daily records. The form will also be used to record the use of any additional contraceptives (e.g. condoms) and coitus within that full 28-day cycle. Site staff will review responses carefully to ensure there are no questions about responses provided by the subject. The information from the daily diaries will be entered in the corresponding CRFs. Each site will retain originals of the completed diaries as source documents and certified copies will be uploaded to the study document repository or EDC at Health Decisions.

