# 10.3.3 Other Contraceptive Use

In the second and third years, participants will record cycle-to-cycle use of any other contraceptive methods. The forms will be used to capture information on other contraceptives used for the six month period between site visits. The information from the forms will be entered in the corresponding CRFs during Visit 6, and Exit. At Calls 2 and Call 3 the site will ask information relative to other contraceptives used since the previous visit in order to prompt subjects to continue completing the forms; however, when the forms are returned at the clinic visits the form responses will be the primary source which will be used for data entry rather than information discussed during the calls that sites may have recorded in the subject's source. Each site will retain originals of the completed forms as source documents and certified copies will be uploaded to the study document repository or EDC at Health Decisions.

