# 11.4 Exit (37 months post-insertion $\pm$ 14 days) or Early Discontinuation Visit

At 37 months or at any time a participant discontinues the study, she will complete Exit Visit procedures as defined in Table 06.

During the Exit visit, collection of information on AEs, concomitant medications, IUD acceptability, and potential concerns will occur. Collection and review of diary or other contraceptive use forms (whichever form type was dispensed at previous visit) will occur with the subjects and IUD acceptability questions will be asked. Study clinicians will verify the presence of the IUD strings; if strings are not present, follow the procedures outlined in Appendix 2.

After all IUD assessments are complete, the clinician will disclose which IUD the subject was using. Those assigned to ParaGard may continue to use that product under the care of primary providers. Those assigned to the test IUD will have the product removed.

All study participants wishing to continue using a different form of contraception after the study will be referred for ongoing contraceptive care within the routine health services, including those continuing use of ParaGard. Options for continued protection from unintended pregnancies should be discussed. A short acting bridge contraceptive (condoms, 1 month of birth control pills, or 1 depo provera shot) should be provided if requested by the subject for use until referral to prevent any pregnancies occurring prior to Telephone Call 4.

Site staff will provide women with a home pregnancy test and instructions to perform the test 17 days (+ 3 days) post-removal and will be scheduled for the pregnancy test confirmation call the same day as testing. During the phone call, follow up regarding ongoing AEs, if applicable, will also be performed. If there are study related AE or new SAEs identified during the phone call, they should be followed until resolution or stabilization.

Table 06: Clinic-Based Exit Visit and Early Discontinuation Visit Procedures

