# 13 PREGNANCY DETERMINATION AND FOLLOW UP

The incidence of pregnancy will be assessed. We will be testing study participants at study visits using urine pregnancy tests and a home pregnancy test 17 days (+ 3 days) after IUD removal. Sites will record information regarding pregnancy on all subjects becoming pregnant during the treatment phase of the study through 17 days after last study product use.

If a subject becomes pregnant during the trial, the Principal Investigator (or designee) must inform Health Decisions of the pregnancy within 24 hours of determination. The subject must be discontinued from the trial, and all procedures scheduled for the Early Discontinuation Visit as detailed in Section 11.6 should be performed. The site will submit a Pregnancy Notification form and End of Study eCRF to Health Decisions within 24 hours of determination. Health Decisions will notify NICHD and FHI 360. Additional pregnancy data will be submitted as it becomes available.

The Investigator will estimate the date of conception based upon results of the following criteria. If there is uncertainty about the dating it will be reviewed with the Medical Monitors.

- Transvaginal ultrasound examination
- Quantitative β-hCG determination
- Last menstrual period (per daily diary information through first year and patient report after first year)
- Pelvic and/or abdominal examination

- Pregnancy outcome
- Investigator estimation in the absence of above criteria

Sites will counsel subjects who become pregnant during the study regarding pregnancy options and refer them for appropriate care. All pregnancies will be monitored until outcome (i.e. 9 months follow-up or until outcome information is obtained through medical records). Information from medical records will also be collected on pregnancy outcome data including maternal or fetal complications, spontaneous abortions, ectopic pregnancies, stillbirths, and live preterm and full-term births.

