## Confidential

-  Urine pregnancy test will be completed in clinic at Screening and during Enrollment prior to the subject being randomized to confirm subject is not pregnant prior to IUD placement if Enrollment occurs on a separate day from Screening.
-  During the Exit visit, the clinician will disclose which IUD the subject was using only after all IUD assessments are complete.
-  If the subject is using ParaGard, ask if she wishes to continue. If not, remove IUD. If the subject is using the test product, remove IUD.
-  Confirmatory quantitative blood pregnancy test should be done if initial urine pregnancy test comes back positive
-  A screening Pap test will be completed for subjects at screening if potential subject is not in compliance with normal standard of care guidelines regarding Pap testing. If additional testing or treatment is required based on Pap results, this should be completed prior to enrollment.
-  Visit 1 distribute 2 diary forms, Visit 2 distribute 2 diary forms, Visit 3 distribute 4 diary forms, and Visit 4 distribute 7 diary forms
-  Visit 2 collect 2 diary forms, Visit 3 collect 2 diary forms, Visit 4 collect 4 diary forms and Visit 5 collect 7 diary forms
-  Visit 5 and Visit 6 distribute 2 Other Contraceptive Use forms
-  Call 2, Visit 6, Call 3, and Exit collect data from Other Contraceptive Use forms
-  Includes subject's levels for pain and bleeding
-  Home pregnancy tests should be provided to subjects at Enrollment and then as needed at other visits with instructions for the subject to complete the test if there is any suspicion that they may be pregnant in between their study clinic visits.
-  Included as part of the Follow-Up Form assessments. At Call 1, Call 2 and Call 3, the follow up form is also referred to as the Telephone Follow Up Form since the Follow Up form information is collected by telephone.
-  Pain will be assessed immediately and 10 minutes after insertion

CCN016 Version #: 03.00 Version Date: 19Dec2018 Page 63 of 76

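### The SAP drops pregnancy-analysis cycles that lack diary data, but the diary ends at month 12, so the rule contradicts the planned year-2, year-3 and three-year Pearl Index

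*SAP*

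**What the plan says.** SAP 7.3.1 builds the Pearl Index denominator in steps. A study cycle is defined without naming a form: "Every 28 study days with information about whether the participant used other contraceptive methods within those 28 study days". The next step adds an exclusion that does name a source: "Study Cycles (described previously) with no diary data will be excluded from the pregnancy analysis". Primary and secondary pregnancy analysis cycles are then drawn from the study cycles that remain. SAP 7.3.2 sets the time horizon: "Analysis will be done for each year of use and cumulatively through year three".

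The protocol uses two instruments, one after the other:

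- Section 10.3.2: "For the first 12 months of use, participants will maintain a daily diary to record bleeding/spotting".
- Section 10.3.3: "In the second and third years, participants will record cycle-to-cycle use of any other contraceptive methods". This is the Other Contraceptive Use form (protocol Appendix 4), which asks about intercourse and other methods for each 28-day interval.
- Section 11.4 treats them as different form types: "Collection and review of diary or other contraceptive use forms (whichever form type was dispensed at previous visit) will occur".
- Appendix 1 gives them separate rows, and its footnote on diary collection stops at the 12-month visit: "Visit 2 collect 2 diary forms, Visit 3 collect 2 diary forms, Visit 4 collect 4 diary forms and Visit 5 collect 7 diary forms".

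The SAP does not mention the Other Contraceptive Use form, and it does not define diary data to include it.

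**The concern.** In this trial the word diary names one form, and that form is not kept after the first year. A programmer who applies the SAP 7.3.1 sentence as it stands would find that essentially every cycle after month 12 has no diary data and would remove it. The year-2 and year-3 Pearl Indices would then have no denominator, and the cumulative figure would be a one-year estimate under a three-year label. Because the sentence refers to the pregnancy analysis as a whole, the cumulative probability curves would stop at about the same point.

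The rule governs the denominator of the only primary endpoint. It should be capable of being carried out as written, without the analyst deciding which of two conflicting instructions to follow.

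**Working it through.** **Inputs**

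- Planned cycles by year: 7,100, 5,700 and 4,900 (footnote to the statistical analysis row of the protocol synopsis). Total 17,700 (protocol 19.1).
- Planning assumptions: 800 women on the test product, 13 cycles per year, 84.3% evaluable, annual discontinuation rate 0.2, 37 months, 51.2% continuing at month 37 (protocol 19.1 and Table 09).
- About 10% of women aged 36-40 (protocol 9.1), so 0.9 × 800 = 720 women count towards the primary analysis.
- Pearl Index and exact Poisson limits as given in SAP 7.3.2.

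**Step 1: reproduce the planned cycles.** Cycles = 720 × 13 × 0.843 × (1 − e^(−λT))/λ, with T = 37/12. Taking λ from 51.2% continuation, λ = −ln(0.512)/T = 0.2171. This gives 17,735 cycles, split 7,093, 5,708 and 4,934. With λ = 0.2 the total is 18,158, and with λ = −ln(0.8) it is 17,590. All are within 3% of 17,700, so the year 2 and 3 cycles are part of the planned denominator.

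**Step 2: reproduce the planned precision.** Pearl Index = 1300 × x/C. Upper limit = 1300 × χ²(0.975; 2x + 2)/(2C). With x = 6 and C = 17,700 the index is 1300 × 6/17,700 = 0.44, with limits 0.16 to 0.96. Table 09 gives 0.4 (0.2-1.0).

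**Step 3: apply the exclusion literally.** Cycles removed: 5,700 + 4,900 = 10,600. Share: 10,600/17,700 = 60%. Cycles left: 7,100.

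**Step 4: precision on what is left.** Pregnancies in excluded cycles leave too, because the exclusion acts before the definition that admits a cycle containing an on-treatment pregnancy.

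| Cycles | Pregnancies | Pearl Index | Upper 95% limit |
|---|---|---|---|
| 17,700 | 6 | 0.44 | 0.96 |
| 7,100 | 0 | 0 | 0.68 |
| 7,100 | 1 | 0.18 | 1.02 |
| 7,100 | 2 | 0.37 | 1.32 |
| 7,100 | 3 | 0.55 | 1.61 |

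How many of 6 pregnancies would fall in year 1 is an assumption. A constant hazard gives 6 × 7,100/17,700 = 2.4. Weighting the planned cycles by the control product's label rates for years 1 to 3 (0.7, 0.3 and 0.6, protocol Appendix 7) gives 6 × 4,970/(4,970 + 1,710 + 2,940) = 3.1. The rows for 2 and 3 pregnancies cover that range.

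**Step 5: the amended size.** Scaling by 880/800 = 1.1 gives 7,810 of 19,470 cycles. On 7,810 cycles the upper limit is 0.93 with 1 pregnancy and 1.20 with 2. On 19,470 cycles it is 0.87 with 6. The share lost is unchanged.

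**Step 6: where the diary really ends.** The forms collected are 2 + 2 + 4 + 7 = 15, and 15 × 28 = 420 days, against 13 × 28 = 364 days for 13 cycles. A cycle just past month 12 may therefore be on a diary form. This hardly changes the loss, but it matters for the wording of a fix.

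**The case against.** The strongest reply is that nobody who reads the whole section would apply the sentence literally. The study-cycle definition names no source, SAP 7.3.2 asks for results through year three, and the sample size counts year 2 and 3 cycles. Protocol 19.2 says that departures from its summary plan will be documented in the SAP, and the SAP documents no dropping of years 2 and 3. The year 2-3 form also repeats the diary's own questions on intercourse and other methods. All of this stands as evidence of intent.

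It does not make the rule usable, because more than one benign reading remains. Diary data may silently include the Other Contraceptive Use form, so that a later cycle without that form is excluded. Or the exclusion may apply only in year 1, so that a later cycle could qualify on information from a follow-up form or telephone call (protocol 10.3.1 and 10.3.3). The two give different denominators whenever forms are missing, and the SAP does not choose.

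Two stronger readings are tempting, and the documents do not support them:

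- A reader might infer that the sponsor means to discard years 2 and 3. The text just cited points the other way.
- A reader might divide all 6 pregnancies by 7,100 cycles and report a Pearl Index of 1.10 (upper limit 2.39). That mixes two readings, since the literal rule also removes the pregnancies in the excluded cycles.

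The last-menstrual-period source is a separate, minor matter. Protocol 13 limits the diary to year 1 for this purpose ("Last menstrual period (per daily diary information through first year and patient report after first year"), and SAP 7.3.1 omits that limit. This bears on dating conceptions and not on exposure.

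**Conclusion.** The point holds as an internal contradiction: the exclusion in SAP 7.3.1 and the yearly and three-year analyses in SAP 7.3.2 cannot both be carried out as written. It is a wrong rule for the primary denominator and more than a missing detail, so it should be corrected before the efficacy analysis is programmed.

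Its size, on the literal reading only, is 60% of planned exposure. An upper limit of about 1.0 would then be reached with 1 pregnancy where the plan allows for 6. These figures rest on the protocol's planning assumptions for 800 women, not on observed data, and on removing pregnancies together with their cycles. If the intended reading is followed, the planned 17,700 cycles and the 0.96 limit stand.

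**What to change.** Replace the exclusion sentence in SAP 7.3.1 with wording such as: *A study cycle is left out of the pregnancy analysis only if neither the daily diary nor the Other Contraceptive Use form has data covering it.* Add that intercourse and other-method status, for both primary and secondary analysis cycles, come from whichever of the two forms covers the cycle.

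Do not split the sources at month 12. A hard cut would lose cycles just past that date that are recorded on one of the 15 diary forms.

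The SAP should also say whether form answers read out at Calls 2 and 3 count when the form itself is never returned. Protocol 10.3.3 settles precedence only for forms that come back. The last-menstrual-period source can be aligned with protocol 13 in the same revision.

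The cost is a few lines of SAP text. Both forms are already collected, so no visit, form or sample size changes.
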